Group 2. 80 patients with PAD will be recruited from in-ward patients and from outpatient vascular clinics. Patients will be recruited by the Vascular Surgery team lead by the Consultant Vascular Surgeon who is the second Academic Supervisor of the PhD student. Patients will be randomised to active INP device (-40mmHg) or placebo INP device (-10mmHg). 20 patients in total will receive the placebo device and 60 will receive the active device. The effects of INP on the measurements described above will be made at baseline (before application of INP), following 1 session of INP (acute effects) and following 4-8 weeks of daily INP. As this is a PhD project, not all patients will undergo 8 weeks' of INP. Based on the initial studies of the shorter 4-week duration, we will be able to examine how many patients will be tested for 8 weeks.

Mechanistic Insights into changes in peripheral blood flow following intermittent negative pressure.

Before application of INP, anthropometric baseline measurements (height, weight) will be taken from all participants at Level 7, Division of Systems Medicine, Ninewells Hospital. For patients, medical notes will be reviewed for clinical characteristic including information on past medical history, drug therapy and blood biochemistry.

[figure not shown]

Figure 1:Flow Chart of study design and measurement techniques.

FLOW-Ox System:

Application of INP will be made using the Flow-Ox machine, a CE marked device provided by Otivio as a gift (Otvio AS, Oslo, Norway) (Figure 1). Participants will be asked to be comfortably clothed and seated (with a 130-degree angle between their hip and knee joint) for 20 minutes prior to the start of the experiment. They will be asked to place a leg into the Flow-Ox chamber which is a molded polyethylene

Mechanistic Insights into changes in peripheral blood flow following intermittent negative pressure.

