For adults who lose capacity their previous wishes will remain legally binding and this will remain valid unless the protocol changes significantly. If this occurs and further consent is required from a participant who has lost capacity, the appropriate person will be asked for their consent. In all cases the CI or delegate will consult with carers and take note of any signs of objection or distress from the participant – the participant will be withdrawn if they raise objection. Where appropriate the participant will be withdrawn from any further clinical intervention and agreement will be sought from a carer to allow data collection.

The informed consent process will be conducted in compliance with TASC SOP07: Obtaining Informed Consent from Potential Participants in Clinical Research

Mechanistic Insights into changes in peripheral blood flow following intermittent negative pressure.

Ineligible and Non-recruited Participants

The reason(s) for ineligibility will be explained to participants and any questions they have will be answered. They will be thanked for their participation in screening.

Withdrawal Procedures

Participants are free to withdraw from the study at any time. If at any time the participant formally withdraws his/her consent for future participation and disclosure of future information, no further evaluations will be performed and no additional data should be collected. Data collected before withdrawal will be retained and used in the study analysis, unless the participant requests otherwise. If participants withdraw during the visit, they will have the option to request that data already collected is not to be used in the study.

STUDY & SAFETY ASSESSMENTS

Patients will undergo their standard care as routine.

PAD patients

Research bloods (40 mls) will be obtained at the research site following informed patient consent and other study procedures such as pain chart, laser imaging, arterial stiffness and ABPI. This usually will occur on the 1st day in the designated research department, Division of Systems Medicine at Ninewells Hospital, and on two follow-up visits, after one INP session and 4 to 8 weeks after daily INP use. We do not envisage that any of these will interfere with their care or are likely to cause any harm. Nevertheless, any adverse events that may potentially be related to the study will be reported to the CI and clinical Vascular Team who will administer appropriate clinical action.

Healthy Volunteers

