Data entry and checking will be undertaken by a single entry with a second look. The data entry and checking process will be decided according to risk. Data that is recorded in the CRF that is not source document in itself will be consistent with the source documents or the discrepancies explained. Checks will be made on all missing values and values out with normal or expected ranges and that values entered

Mechanistic Insights into changes in peripheral blood flow following intermittent negative pressure.

are of the correct type: i.e. numerical instead of text. Logical checks will be performed to ensure consistent reporting between relevant fields and that there are no differences between fields. Data checking will continue until all missing data and/or inconsistent values have been corrected or clarified. When data checking is complete, with no outstanding data queries, the database will be locked, using the Protect Worksheet function of EXCEL, as FINAL RESULTS. The EXCEL spreadsheet will remain archived on the Dundee University secure server for 5 years for the retention of essential documents, thereafter it will be deleted.

STATISTICS AND DATA ANALYSIS

Sample Size Calculation

As this is a PhD project exploring mechanisms of vascular changes, precise power calculations have not been obtained. The results from this PhD project will guide us regarding subsequent power calculations. However, based on our previous work exploring mechanisms of changes in vascular function using various interventions, n=25 subjects will provide at least 80% power and 5% significance to detect a 20% before and after difference within subjects in the vascular function markers proposed in this study.

Proposed Analyses

Changes in blood flow and endothelial function in the lower limbs using laser Doppler perfusion imaging and iontophoresis will be compared primarily within each group and also between patient groups at baseline, after 1 INP session and after the last INP (4 to 8 weeks) is applied. The primary outcome measure will be the change in peak blood flow response to acetylcholine and sodium nitroprusside.

Data will be analysed using widely available statistical analysis software such as SPSS. Analytical methods will include t-tests, chi-square, ANOVA, correlation and regression as appropriate.

Mechanistic Insights into changes in peripheral blood flow following intermittent negative pressure.

STUDY MANAGEMENT AND OVERSIGHT ARRANGEMENTS

Study Management

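### The three-visit outcome has no named repeated-measures method or missed-visit rule; a mixed model on all visits would protect the late change if dropout follows acute response

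*Combined protocol and SAP*

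**What the plan says.** Study & Safety Assessments schedules three assessments for each participant: at baseline, after one session, and after repeated use (4 to 8 weeks in PAD patients, up to 5 days in healthy volunteers). Under Proposed Analyses the measurements "will be compared primarily within each group and also between patient groups at baseline, after 1 INP session and after the last INP", and "The primary outcome measure will be the change in peak blood flow response to acetylcholine and sodium nitroprusside". The method is a single sentence: "Analytical methods will include t-tests, chi-square, ANOVA, correlation and regression as appropriate". It does not say whether t-tests are paired, whether ANOVA is of the repeated-measures kind, how three correlated visits enter one analysis, or what happens when a visit is missed.

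Two other statements bear on this. Withdrawal Procedures states that "Data collected before withdrawal will be retained and used in the study analysis, unless the participant requests otherwise". Sample Size Calculation says that "precise power calculations have not been obtained" but adds that "n=25 subjects will provide at least 80% power and 5% significance to detect a 20% before and after difference within subjects", which is a paired, two-occasion statement.

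**The concern.** The choice between complete-case and available-case analysis is left until the data exist, and under Randomisation the researcher knows the allocation. Missed last visits are plausible: the late assessment follows weeks of home use, an hour twice a day, and the protocol plans weekly contact to support adherence.

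Classical repeated-measures ANOVA, the listed method that most naturally takes three occasions, needs all three values. A patient who leaves after the acute test is then lost from the acute comparison as well. Separate paired t-tests avoid that. Their late contrast, however, rests only on those who returned. If patients with a weaker acute response return less often, the returners are a favourable selection and the late change is too large. The acute values that could correct this have been collected but are not used.

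**Working it through.** **Inputs from the documents.** Three visits; within-group change as the primary comparison; "20 patients in total will receive the placebo device and 60 will receive the active device"; n=25, 80% power, 5% significance, 20% change.

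**Assumed, because the documents are silent.** Two-sided test; correlation 0.6 between any two visits; equal SD at each visit; about 21% of last visits missing; acute effect 60% of the late effect; and the dropout rule in step 3.

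**1. The plan's own figure.** It cannot be reproduced, because no SD of the change is given. Solving the paired t-test for 80% power at n=25 gives a standardised change of 0.584, so the implied SD of the change is 20/0.584 = 34.2%.

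**2. True effects, in single-visit SD units.** The SD of a change is √(2(1−0.6)) = 0.894. The late effect is 0.584 × 0.894 = 0.522, and the acute effect is 0.6 × 0.522 = 0.313.

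**3. Simulation.** 60 active patients, 4,000 runs. The log-odds of missing the last visit fall by b per SD of acute change, with the intercept set to give about 21% missing.

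| Dependence of dropout on acute change | Acute, complete cases (true 0.313) | Late, available pairs (true 0.522) |
|---|---|---|
| Strong (b = 0.8) | 0.449 | 0.589 (+13%) |
| Half (b = 0.4) | 0.386 | 0.559 (+7%) |
| Weak (b = 0.2) | 0.350 | 0.541 (+4%) |
| None (b = 0) | unbiased | unbiased |

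Under strong dependence the likelihood analysis of all visits gives 0.313 (acute) and 0.521 (late). The paired t-test of baseline against one session gives 0.312, so for the acute change it is as good as the mixed model.

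**4. Check by formula.** With equal correlations, the slope of late change on acute change is (1−ρ)/(2(1−ρ)) = 0.5. Half of the acute selection therefore passes to the late change: 0.522 + 0.5 × (0.449 − 0.313) = 0.590, against 0.589 simulated.

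**5. Size against sampling error.** About 0.79 × 60 = 47.4 patients have a last visit. The SE of the late change is 0.894/√47.4 = 0.130, and the bias of 0.067 is about half of that.

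**6. If dropout is random.** Complete-case ANOVA costs precision only: the acute SE rises by √(60/47.4) = 1.12, about 12%.

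**7. A harsher dropout rule.** Take a true change of 20% at both visits, SD of change 34.3%, correlation 0.5 or 0.7, and a dropout score that is half acute change and half noise by variance. The late change from available pairs is then about 24 with 20% missing and 26 with 30% missing; the mixed model gives about 20. With random dropout both give 20, and the mixed model's estimate is only about 2 to 5% less variable.

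**The case against.** A reader might infer that the listed methods force a choice between dropping everyone with a missed visit and ignoring the pairing. They do not. A paired t-test of baseline against one session is a t-test; it keeps the pairing, keeps everyone with those two visits and is unbiased here. Regression is listed too. The text leans towards pairing: the outcome is a change, comparison is primarily within group, the sample-size statement is within-subject, and data before withdrawal are to be used. The acute bias therefore needs complete-case ANOVA, which the plan does not name, together with response-dependent dropout. All of this stands.

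The late bias rests on an assumed mechanism. Nothing in the documents shows that poor acute responders leave more often, and patients do not feel a laser Doppler response to acetylcholine or nitroprusside. Even the strong case in the table amounts to about half a standard error. This also stands, and it limits the weight of the point. It does not remove it: the direction of the error is known if the mechanism operates, and correcting it costs almost nothing.

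**Conclusion.** The point holds as a worthwhile, low-cost improvement. For the late change, paired t-tests on available pairs overstate the effect by about 13%, 7% or 0% under strong, half-strength or no dependence of dropout on acute response, given 60 patients, correlation 0.6 and about 21% of last visits missing. The mixed model removes this only if data are missing at random, that is, if dropout depends on values already observed. For the acute change it gains nothing over a paired t-test; the gain is over complete-case ANOVA, which would also conflict with Withdrawal Procedures.

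It should not be inferred that a mixed model preserves the stated 80% power. That figure is for a paired comparison of 25 subjects with an unstated SD. At the implied SD, paired power with complete data is 99% at n=60, 95% at n=40 and 70% at n=20, so the placebo group is below 80% whatever the model. A fall from 80% to 44% at correlation 0.6 would occur only with an unpaired test at n=25, and the plan does not say it will use one. At n=60 even that test would have 81%.

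**What to change.** For the continuous outcomes, replace the methods sentence in Proposed Analyses with wording such as: a linear mixed model with unstructured covariance over the three visits and fixed effects for group, visit and group-by-visit, fitted to all available visits; the last visit is identified by its actual duration (4 or 8 weeks in PAD patients, up to 5 days in healthy volunteers); the contrasts are one session minus baseline and last visit minus baseline. Name explicitly paired t-tests on available pairs as supporting analyses. State that the model assumes data missing at random, and report the number of missed visits by group. Make no claim about power on the strength of this change.

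SPSS, the software the plan gives as its example, fits the model. The cost is wording and slightly more analysis work; no extra data or patients are needed.

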PAD attenuates both life expectancy and the quality of life as it increases the risk of cardiovascular diseases (CVD) such as myocardial infarction and stroke (1). Evidently PAD and CVD share common risk factors which include; age, smoking, dyslipidaemia, hypertension and diabetes mellitus (2). The risk of CVD related mortality can be reduced by risk factors modifications; prescribing antiplatelet therapy, ACE inhibitors and statins to PAD patients (1). Although, PAD has many clinical presentations it can be categorised into three classes: intermittent claudication (IC), critical limb ischaemia (CLI) and asymptomatic disease (3). IC is the typical presenting symptom and is usually perceived as muscle fatigue, cramps or pain in the lower limbs (1)(3). The characteristic symptom of claudication is elevated pain upon exercise and its resolution by sufficient rest (1). In fewer cases, patients may also experience CLI, which is clinically recognised as rest pain and defined phenotypically by either ulceration and gangrene of the foot, or physiologically by a toe systolic blood pressure of <30mmHg or an ankle systolic blood pressure of <50mmHg (1)(3).

All first line treatment modalities for PAD aim to impede diseases progression and augment blood flow (4). These include behavioral modifications that aid risk factors regression and enhance exercise performance (4). If behavioral alterations fail to deliver expected results, an alternative line of treatment is revascularisation through open surgery or endovascular surgery (4). While the innovation of endovascular techniques has transformed the field of vascular treatment in PAD, it has not changed the selection of individuals that are expected to benefit from revascularization and unsurprisingly this line of therapy is proven to be highly invasive and inadequate for many PAD patients (3)(4). There remains a need for novel treatment options that can help treat PAD in a non-invasive manner. Intermittent negative pressure (INP) is one such non-invasive technique that aims to increase blood flow in ischaemic limbs. Although the idea that air pressure can be regulated to increase distal circulation was first described by

Mechanistic Insights into changes in peripheral blood flow following intermittent negative pressure.

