access measures via user names and passwords. Personal data concerning health will not be released except as necessary for research purposes including monitoring and auditing by the Sponsor, its designee or regulatory authorities providing that suitable and specific measures to safeguard the rights and interests of participants are in place. The CI and trial staff will not disclose or use for any purpose other than performance of the trial, any personal data, record, or other unpublished, confidential information disclosed by those individuals for the purpose of the trial. Prior written agreement from the Sponsor will be required for the disclosure of any said confidential information to other parties. Access to collated personal data relating to participants will be restricted to the CI and appropriate delegated trial staff. Where personal data requires to be transferred, an appropriate Data Transfer Agreement will be put in place. Published results will not contain any personal data that could allow identification of individual participants.

Insurance and Indemnity

The University of Dundee and Tayside Health Board are Co-Sponsoring the study.

Insurance –The University of Dundee will obtain and hold a policy of Public Liability Insurance for legal liabilities arising from the study.

Tayside Health Board will maintain its membership of the Clinical Negligence and Other Risks Insurance Scheme (“CNORIS”) which covers the legal liability of Tayside in relation to the study.

Where the study involves University of Dundee staff undertaking clinical research on NHS patients, such staff will hold honorary contracts with Tayside Health Board which means they will have cover under Tayside’s membership of the CNORIS scheme.

Indemnity The Co-Sponsors do not provide study participants with indemnity in relation to participation in the Study but have insurance for legal liability as described above.

ADVERSE EVENTS DEFINITIONS

| | |
|-----------------------------|---|
| Adverse Event (AE) | Any untoward medical occurrence in a clinical research participant which does not necessarily have a causal relationship with study participation |

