| Serious Adverse Event (SAE) | A serious adverse event is any untoward medical occurrence that: 
• results in death• is life threatening• requires hospitalisation or prolongation of existing hospitalisation• results in persistent or significant disability or incapacity• is a congenital anomaly or birth defect• Or is otherwise considered serious |

RECORDING AND REPORTING AE

All AEs and/or SAEs will be recorded on the AE Log in the CRF and will be assessed for severity by the clinician from the research team. AEs/SAEs will be recorded from the time a participant consents to join the study until the participant's last study visit. The Investigator will make a clinical judgment as to whether or not an AE is of sufficient severity to require the participant's removal from the study. A participant may also voluntarily withdraw from treatment due to what he or she perceives as an intolerable AE. If either of these occurs, the participant should, if required, be offered an end of study assessment and be given appropriate care under medical supervision until symptoms cease, or the condition becomes stable. AEs/SAEs will be followed up until 30 days after participant's last visit.

The CI or delegate will ask about the occurrence of AEs/SAEs and hospitalisations at every visit during the study. **SAEs which are both unexpected and related to study participation** will be submitted on an HRA NCTIMP Safety Report form to the REC by the CI, within 15 days of becoming aware of the SAE, and copied to the Sponsor Research Governance Office.

Worsening of the condition under study will not be classed as an AE, but will be defined as an outcome. Pre-specified outcome(s) will not be classed as an AE but as an outcome. Elective admissions and hospitalisations

Mechanistic Insights into changes in peripheral blood flow following intermittent negative pressure.

for treatment planned prior to randomisation, where appropriate, will not be considered as an AE. However AEs/SAEs occurring during such hospitalisations will be recorded.

ANNUAL REPORTING REQUIREMENTS

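### Worsening PAD is taken out of the adverse events and assigned to an outcome that the protocol never defines, so non-serious limb events are neither logged nor counted, and SAE handling is unclear

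*Combined protocol and SAP*

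**What the plan says.** Recording and Reporting AE contains two adjacent exemptions. The first is "Worsening of the condition under study will not be classed as an AE, but will be defined as an outcome". The second is "Pre-specified outcome(s) will not be classed as an AE but as an outcome". A third exemption covers elective admissions and hospitalisations "for treatment planned prior to randomisation, where appropriate, will not be considered as an AE".

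Adverse Events Definitions describes an AE as "Any untoward medical occurrence in a clinical research participant which does not necessarily have a causal relationship with study participation". An SAE has its own definition with a list of seriousness criteria, one of which is "requires hospitalisation or prolongation of existing hospitalisation".

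AEs and SAEs "will be recorded on the AE Log in the CRF and will be assessed for severity by the clinician from the research team". SAEs that are both unexpected and related go to the REC within 15 days. The section also provides for detection: "The CI or delegate will ask about the occurrence of AEs/SAEs and hospitalisations at every visit during the study".

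Proposed Analyses names one primary outcome, the change in peak blood flow response to acetylcholine and sodium nitroprusside.

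**The concern.** An exemption for disease progression is coherent when the exempted events are captured somewhere else. Here the sentence sends them to an outcome, so the outcome sections ought to contain it. If they do not, a limb event attributed to PAD leaves the safety record and enters no other.

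This matters in this trial for four reasons.

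- The device acts on the lower leg of patients with PAD, who use it at home for 4 to 8 weeks (Study Design; FLOW-Ox System). A harmful device effect and natural progression could look alike.
- Ward patients are eligible and wounds are not an exclusion (Study Population). The Background describes critical limb ischaemia, one of its classes of PAD, as "clinically recognised as rest pain and defined phenotypically by either ulceration and gangrene of the foot". Worsening can therefore include serious events.
- The Background reports no known side effects. On that text a serious device-related limb event would be unexpected, and relatedness would decide whether the REC is told.
- The researcher knows the allocation (Randomisation), and no role is named to decide that an event is worsening.

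At stake is the completeness of the limb-safety record.

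**Working it through.** No arithmetic applies, and the plan gives no figure on this point to reproduce. The check is a trace through the text.

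**1. Is there an outcome to receive the event?**
- Primary outcome (Proposed Analyses): a perfusion response, not a clinical event.
- ABPI and pain chart (specific aims under Study Objectives): values before and after INP, with no threshold or event definition for worsening.
- Wounds (Laser Doppler Imaging): photographed and measured at each assessment, but used in no stated aim or analysis.
- Critical limb ischaemia (Background): described, but not used as an outcome or event definition.

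No outcome, aim or analysis counts discrete limb events such as new ulceration, gangrene, unplanned revascularisation or amputation.

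**2. Where do the safety routes start?** The AE log with its severity grading, the judgement on removing a participant, follow-up to 30 days after the last visit and the REC report (Recording and Reporting AE) all start from an AE or SAE. Notification of the CI and vascular team (Study & Safety Assessments) is worded for adverse events.

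**3. A non-serious event.** Take an enlarging ulcer on the treated leg that is attributed to PAD. The first exemption takes it out of the AE class, so it is not logged. Its size may be measured, but no analysis uses it. It is neither an AE nor a counted outcome.

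**4. A serious event.** Take an unplanned admission for limb ischaemia. Two readings are open.
- It remains an SAE. The SAE definition stands alone, and the exemption mentions only AEs, in a section that elsewhere writes AEs and SAEs together when it means both.
- It is exempt. The sentence on elective admissions uses the term AE for hospitalisations, which suggests that AE there includes serious events.

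The text does not choose between them.

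**5. Detection.** Weekly contact (FLOW-Ox System), the question about hospitalisations, the collection of diagnosis and treatment (Data Collection) and the recording of incidents (Study Management) may bring an event to notice. None of them states a step for judging whether it relates to the device. Annual Reporting Requirements forwards additional safety reports if there are any, but nothing says that worsening PAD generates one.

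**6. Relatedness in general.** For every logged AE the only written assessment is severity. Relatedness appears as a condition for the REC report and in the phrase about potentially related events in Study & Safety Assessments. This gap is not confined to worsening PAD.

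**7. Who is exposed.** 40 randomised active + 20 randomised placebo + 20 non-randomised active = 80 PAD patients. The exemption applies to all of them.

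**The case against.** The strongest reply is that a reader might infer that limb events have no safety-reporting route at all, and that the text does not support this. That is right. The SAE definition is free-standing, so the narrow reading in step 4 is tenable. SAE reporting is unclear, not absent.

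A reader might also infer that this sentence causes the missing relatedness assessment. It does not, because no AE has a written relatedness step. Nor is the record without an owner: the CI is responsible for the completeness and consistency of the CRF (Data Management System) and for the study data (Study Management). What is missing is a named role for the specific decision that an event is worsening.

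It can also be said that the two exemptions merely overlap, and that worsening is meant to be seen through perfusion, ABPI, pain and wound measurements. That is possible, but the protocol does not say so. Those measurements would not record an amputation or a new area of gangrene as an event, and wound size has no analysis.

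A clear injury from the boot remains an AE under the general definition, so the point is limited to events where device effect and progression are hard to separate. The CRF and SOPs are not in the documents and may say more. The point concerns only what the protocol specifies.

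**Conclusion.** The concern holds in this form. The protocol removes worsening PAD from the AEs and promises an outcome that it does not define. As written, a non-serious limb event attributed to progression is neither logged nor counted, and the handling of a serious one is open to two readings. This is more than missing detail, because following the rule can leave the limb-safety record incomplete. The protocol should be amended.

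The size is not quantified. The documents give no limb-event rate, and the share of events that would be classed as progression is unknown, so no rate is assumed here. The primary outcome is not affected. It would go too far to conclude that serious limb events are excluded from REC reporting.

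There is a separate, minor clarification: treatment planned before randomisation has no reference date for the 20 patients who are not randomised. That concerns a different sentence and does not measure this point.

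**What to change.** The change concerns recording and reporting only. Reconcile Recording and Reporting AE with the outcome sections as follows.

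- (a) Limit the exemption to changes in the scheduled perfusion, ABPI and pain-score measurements, and name these as the outcomes meant.
- (b) State that any PAD-attributed event meeting an SAE criterion is recorded and assessed as an SAE.
- (c) Record other unplanned, clinician-identified limb events, including a new or enlarging wound, on the AE log with date, leg (treated or untreated), device and relatedness.
- (d) Name the role that classifies events and judges relatedness, for all AEs.
- (e) List the events descriptively for randomised active, randomised placebo and non-randomised active patients separately.

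The existing exclusion for elective and previously planned treatment can stay. A reference date for the 20 non-randomised patients can be added in the same amendment.

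The cost is a few more AE and SAE entries, most of which will reflect natural progression, some CRF fields and a short listing. The protocol amendment needs Sponsor, REC and NHS R&D approval under the section on amendments and breaches.
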